SMART Trial: Steroid Dosing by bioMARker
Guided Titration in Critically Ill Patients
With Pneumonia

NCT03852537

January 4, 2021

SMART trial: Steroid dosing by bioMARker guided Titration in critically ill patients with Pneumonia.

IRB number:-18-010925

Principal Investigator: [name] M.D

Co-Principal Investigator: [name] M.D.

Co-investigators: [name] M.D, [name] M.D, [name] Pharm.D.

Statistician: [name] M.S

Protocol Version: 8; 1/4/2021

Abstract

Pneumonia is the most common cause of acute hypoxemic respiratory failure. The limited and variable use of corticosteroids in critically ill patients with pneumonia is largely due to an inability to identify patients that will benefit from the use of anti-inflammatory medications. Increased levels of pro-inflammatory mediators are a prominent feature of pneumonia and previous studies have tracked the effect of steroids on inflammatory biomarkers or, more recently, used biomarkers (i.e. C Reactive Protein -CRP) to enroll patients in to clinical trials. The objective of this prospective, single-center pilot trial is to compare individualized, biomarker concordant vs usual care in patients with pneumonia and acute hypoxemic respiratory failure identified in the emergency department whose bedside physicians intend to provide adjunctive corticosteroid treatment. These data will be used to assess feasibility, refine the protocol, and calculate the sample size in preparation for a larger pragmatic clinical trial comparing the two strategies.

Research Plan

I. Specific Aims

Specific Aim 1: To assess the feasibility, safety and preliminary efficacy of individualized, biomarker-guided corticosteroid dosing compared to usual care in critically ill patients with community acquired pneumonia and acute hypoxic respiratory failure. We hypothesize that, compared to usual care; individualized, biomarker-guided corticosteroid dosing will lead to:

- Lower cumulative exposure to corticosteroids
- Lower incidence of adverse events (hyperglycemia, delirium, and nosocomial infections)
- Improvement in pulmonary organ function based on requirements for oxygen and advanced respiratory support
- Reduced hospital length of stay

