CRP/procalcitonin who were treated with steroids or patients with a low CRP/procalcitonin who were not treated with corticosteroids), versus treatment that was biomarker-discordant. The threshold for an elevated CRP was 150mg/L and the threshold for an elevated procalcitonin was 2.2ng/ml. After adjusting for severity of illness, early (within 12 hours of ICU admission) steroid administration in patients with pneumonia or ARDS was associated with decreased persistence or progression of pulmonary and other organ failures, reduced hospital and ICU length of stay and decreased hospital mortality(table 1). Patients with biomarker-concordant and biomarker-discordant corticosteroid treatment had similar baseline severity of illness. Biomarker-concordant corticosteroid treatment was associated with faster recovery of hypoxemia (table 2). No significant differences in mortality or hospital/ICU length of stay were seen between the biomarker-concordant versus the biomarker discordant group.

Table1. Impact of early corticosteroid use on outcomes in ICU patients with pneumonia and ARDS

	Steroids ≤ 12h after ICU admission (N=1047)	Steroids > 12h after ICU admission(N=567)	P value
SOFA Day 1	5 (3-8)	6 (4-8)	0.006
SOFA Day 2	4 (2-6)	5 (3-8)	<0.001
SOFA Day 3	4 (2-7)	5 (3-8)	0.009
PaO ₂ /FiO ₂ at ICU admission	173 (117-250)	161 (108-240)	0.16
PaO ₂ /FiO ₂ after 24h	196 (143-265)	183 (122-255)	0.03
PaO ₂ /FiO ₂ after 48h	209 (145-284)	191 (129-255)	0.03
ICU length of stay	1.98 (1.07-4.0)	3.69 (1.95-7.24)	<0.001
Hospital Length of stay	7.57 (4.55-14.07)	10.4 (6.08-20.8)	<0.001
ICU Mortality	102 (9.7%)	69 (12.2%)	0.15
Hospital Mortality	188 (17.9%)	132 (23.3%)	0.01

Table 2: Impact of steroid use that was concordant versus discordant with markers of inflammation on outcomes in critically ill patients with pneumonia

	Biomarker Concordant (N=130)	Biomarker Discordant(N=114)	P value
FIO ₂ at ICU admission	40 (30, 60)	40 (30, 60)	0.47
FIO ₂ Day 2	35 (28, 50)	40 (31, 50)	0.07
FIO ₂ Day 3	31 (21, 40)	37 (29, 50)	0.004
FIO ₂ Day 4	28.0 (21.0, 37.5)	35 (28, 50)	<.001
FIO ₂ Day 5	28 (21, 36)	28 (24, 45)	0.03
ICU free days (Median estimate (95%CI)	1.97 (-0.50, 4.45)	0.00 (Ref)	0.12
Hospital free days (Median estimate (95%CI)	1.79 (-0.98, 4.57)	0.00 (Ref)	0.21
ICU Mortality (Hazard Ratio with 95% CI)	0.93 (0.31, 2.74)	1.00 (Ref)	0.89
Hospital Mortality (Hazard Ratio with 95% CI)	0.75 (0.36, 1.59)	1.00 (Ref)	0.45
Delirium	36 (27.7%)	34 (29.8%)	0.71

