In the individualized, biomarker-concordant arm, all patients will receive steroids once at the time of admission, then a daily morning dose. In order to account for varying turnaround time at different laboratories, CRP levels will be drawn with early morning labs, and used to determine the steroid dosing for the day. Patients will receive daily CRP measurements for the first 5 days of the hospitalization, or until hospital discharge. Steroid administration will be facilitated using standardized computerized physician order entry. Steroid order sets will include 6 hourly point of care glucose monitoring, and an insulin sliding scale for glucose levels to facilitate glucose management. The need for insulin drip will be determined by the treating physician. Additional testing including serum and urine ketones will be informed by the glucose level, serum anion gap and bicarbonate levels in routine basic metabolic panels and determined by the treating physician. Glucose levels, new or worsening infections within 30 days of start of steroid (positive blood/sputum/urine culture) and Confusion Assessment Method in the ICU will be documented in case report forms.

In the usual care arm, patients will receive daily CRP measurements for the first 5 days of the hospitalization, or until hospital discharge. However, these CRP measurements will not be accessible to the treating physicians.

An oxygen titration protocol will be utilized to standardize oxygen weaning in both arms (please see appendix).

Daily Troponin measurements will be added in both arms

Primary outcomes:

- Feasibility: a percentage of eligible patients adhered to the timely initiation and daily treatment according to ESICM/SCCM clinical practice guideline (control group) or biomarker concordance (intervention group)

Secondary outcomes

- Death
- Progression of disease as defined by the need for high flow nasal cannula oxygen, noninvasive or invasive ventilation. Given the proliferation of high flow nasal cannula oxygen use in lieu of mechanical ventilation, instead of ventilator-free days we opt for

using advanced respiratory support free days where “advanced respiratory support” includes both invasive and noninvasive mechanical ventilation and the high flow nasal cannula oxygen.

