- Evolution of respiratory and other organ failures measured by SOFA at time of ICU admission, after 24 hours, after 48 hours and after 72 hours and by the organ failure free days. In the absence of daily arterial blood gas analysis, for respiratory component of SOFA, $\text{PaO}_2/\text{FiO}_2$ ratio will be replaced by $\text{SpO}_2/\text{FiO}_2$ ratio
- Need and duration of vasopressors and inotropes use (based on cardiovascular SOFA sub-score)
- New onset/worsening arrhythmias
- Evidence of myocardial injury determined by daily troponin peak and/or new diagnosis of LV dysfunction ($\text{LVEF} < 40\%$) or new diagnosis of cor pulmonale (\geq moderate RV dysfunction)
- Re-hospitalization for a primary cardiovascular diagnosis within 30 days
- Side effects of steroid (Safety) including
 - Hyperglycemia and its complications- Diabetic ketoacidosis (DKA) and Hyperosmolar hyperglycemic syndrome (HHS), the need for insulin
 - Delirium (measured by CAM-ICU) and
 - New infections in patients with pneumonia and/or ARDS
- Length of ICU and hospital stay
- Time to discontinue oxygen or return to baseline oxygen use
- Requirement and duration of non-invasive and invasive mechanical ventilation
- ICU, and 30, 60 and 90-day mortality
- Discharge, 30, 60, and 90-day disposition (home vs other)

C. Sample Size and Power: In this pilot study, we do not have the power to test the efficacy of the intervention on patient-centered outcomes. However, this pilot data will provide us with potential effect size data necessary for sample size determination for the future phase II/III study.

D. Data Collection: Case Report Forms will be completed by research coordinators and entered in a REDCap database.

E. Data Handling:

- Protected health information will be preserved by having patient data be de-identified and given a study number.
- This data will be recorded using REDCap and JMP. Any written data will be stored in storage files in a locked access building.
- Data will only be accessible to investigators/participating personnel.
- The computers where the data will be stored meet strict security requirements imposed by Mayo Clinic.
- No data containing PHI will be transported on data sticks or laptops without being encrypted or password protected.
- No hardcopy information containing PHI will be transported/removed from the Mayo campus.
- Any hard copies of archival source documentation will be stored in a locked, secure location only accessible to the study personnel.

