- No data will be disclosed to another institution and all identifiers linking to the patient will be destroyed after data collection is complete.

f. Data Analysis

Aims 1 and 3: Continuous outcomes will be compared between treatment arms using linear regression and binary outcomes using chi-square or fishers exact tests. Secondary outcomes will be tested without adjustment for multiple comparisons. Data from this study, including estimated effects of the intervention and sample variation in outcomes, will provide valuable information to plan a well-powered subsequent phase II trial.

Aim 2: The correlation between CRP levels and corticosteroid dosing in those who receive individual-dose steroids versus usual care will be examined using Pearson's correlation coefficient. The effect of CRP levels on the secondary outcomes will be evaluated using multivariable analysis adjusting for severity of illness. The data from this study will help evaluate the usefulness of CRP as a predictive and prognostic enrichment tool and thus help inform and refine the thresholds for initiation, titration and discontinuation of corticosteroids in the subsequent larger study.

Decision to proceed with a larger study: The decision to proceed with a phase II/III study will be based on the following criteria:

- Ability to enroll an adequate number of eligible patients early in the course of illness. The expected hurdles include delayed identification of potentially eligible patients, provider/patient refusal, non-adherence to protocol, and inability to obtain CRP levels in a timely manner.
- Safety; i.e. absence of significant adverse events.

- Preliminary efficacy: ability to show reduction in steroid use, reduced episodes of hyperglycemia and favorable trajectory of pulmonary organ dysfunction.

The data collected will be essential to adequately plan the future study, estimate power and sample size, refine exclusion/inclusion criteria and determine the number and characteristics of future study sites.

g. Feasibility and Time Frame:

We believe that our project is feasible in the time frame of the grant; we hope to use the preliminary data generated from this pilot study to decide about moving forward with a phase II/III study involving a larger study group and more centers (Table 5).

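### The lung trajectory that feeds the decision to proceed has no named score, and the continuous SpO2/FiO2 needed to score it is not itself analysed

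*Combined protocol and SAP*

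**What the plan says.** Section IV.B, Secondary outcomes, gives the repeated organ measure as "Evolution of respiratory and other organ failures measured by SOFA at time of ICU admission, after 24 hours, after 48 hours and after 72 hours", continuing "and by the organ failure free days". The item then adds a substitution: "In the absence of daily arterial blood gas analysis, for respiratory component of SOFA", SpO2/FiO2 takes the place of PaO2/FiO2. No item makes FiO2 or SpO2/FiO2 an outcome in its own right.

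Other lung outcomes are listed in the same section, among them days free of advanced respiratory support, "Time to discontinue oxygen or return to baseline oxygen use", and the need for and duration of ventilation.

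Section III, Table 2, is the preliminary evidence for biomarker-concordant treatment. Its favourable result is on FiO2 by day, which the text reads as quicker recovery from hypoxemia. CRP is to be measured daily for the first 5 days in both arms (section IV.B, Protocol).

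Section IV.f names linear regression for continuous outcomes under Aims 1 and 3, with no repeated-measures model and no baseline covariate. Its list of criteria for going on to a larger study includes a "favorable trajectory of pulmonary organ dysfunction". Aim 2 promises trajectories of CRP and of pulmonary and non-pulmonary organ failure. The enrolment target is 44 (sections IV.A and IV.i).

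**The concern.** A criterion for the next trial depends on a trajectory that the plan does not define. Only one lung-related measure is repeated on a schedule, and it can be analysed in two ways that behave very differently. The total mixes the lung with several other organs. The respiratory component is specific to the lung but coarse. The finer quantity, SpO2/FiO2, must be obtained to score that component whenever there is no blood gas, yet no analysis of it is planned.

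Two further gaps follow. Scheduled SOFA ends at 72 hours, while the CRP series it should be read against runs for 5 days. SOFA also starts at ICU admission, although patients are identified in the emergency department and Aim 3 covers patients admitted to hospital, so no start time is given for anyone who does not enter the ICU.

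At stake is what the pilot hands on. Sections IV.C and IV.f say it will supply effect sizes and variation for planning. The planned analyses supply neither for the measure that carried the preliminary signal, even though much of the raw ratio would be on file. The go or no-go reading could also change with a choice of score made after the data are seen.

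**Working it through.** The plan contains no power calculation to reproduce, so the first step is to check Table 2 against itself.

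**Inputs from the documents.** FiO2 as median (quartiles), concordant (N=130) v discordant (N=114):
- Day 3: 31 (21, 40) v 37 (29, 50), P=0.004
- Day 4: 28.0 (21.0, 37.5) v 35 (28, 50), P<.001
- Day 5: 28 (21, 36) v 28 (24, 45), P=0.03

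SOFA on day 3 (Table 1): quartiles 2-7 and 3-8. SpO2 target 90-95% (Appendix 1). Total enrolment 44.

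**Assumptions, not in the documents.** Equal allocation with no loss (22 per arm), and a two-sided 0.05 test.

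**Step 1: is the signal in the table?** Take SD = (Q3 - Q1)/1.349.
- Day 4: SDs 16.5/1.349 = 12.2 and 22/1.349 = 16.3. SE = √(12.2²/130 + 16.3²/114) = 1.86. The median difference 7 gives z = 3.8, p about 0.0002, in line with <.001.
- Day 3: SDs 14.1 and 15.6, SE = 1.91, difference 6, z = 3.1, p about 0.002, against 0.004.
- Day 5: the medians are equal. The mean of the three quartiles differs by 97/3 - 85/3 = 4.0, p about 0.02, against 0.03.

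These are rough for skewed data, but they agree with the table.

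**Step 2: continuous FiO2 with 22 per arm.** Power ≈ Φ(d√(22/2) - 1.96).
- Day 4: pooled SD = √((12.2² + 16.3²)/2) = 14.4, d = 7/14.4 = 0.49, power 36%. With the quartile-mean difference 8.83, d = 0.61 and power 53%.
- Day 3: d = 6/14.8 = 0.40, power 27%. With the quartile-mean difference 8.0, d = 0.54 and power 43%.
- Day 5: d = 4.0/13.5 = 0.30, power 16%.

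For 80% power the numbers per arm are 55-97 (day 3), 42-67 (day 4) and about 180 (day 5). At 22 per arm the effect detectable with 80% power is (1.96 + 0.84)√(2/22) = 0.84 SD.

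**Step 3: the same effect seen through each score.** FiO2 was simulated from the Table 2 quartiles with the maximum set at 60, 80 or 100%, and SpO2 drawn within 90-95%. The ratio was banded 0-4 under three assumed sets of cut-points (512/357/214/89, 400/315/235/150, 450/300/200/100). For the total, other-organ points with an assumed SD of 2 to 3.5 were added.

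| Measure, 22 per arm | Power, days 3-4 |
|---|---|
| Continuous SpO2/FiO2 | about 37-55% |
| Respiratory item alone | about 23-54% |
| SOFA total | about 6-16% |

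With a different upper tail for FiO2 and a tighter other-organ spread, the total reaches at most 21% on day 3 and 23% on day 4.

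**Step 4: a check on the total without simulation.** Table 1 implies SD = 5/1.349 = 3.7 for day 3 SOFA. A shift of 0.5 point is d = 0.5/3.7 = 0.135, power about 7%. A full point is d = 0.27, power about 14%.

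All these are single-day comparisons. The gain from baseline adjustment and repeated measures depends on within-patient correlation, which the documents do not give, so it is not counted.

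**The case against.** The strongest reply is that the plan never says the total will be analysed. The SOFA item names respiratory failure first and defines its component, the next item uses a cardiovascular sub-score, Aim 2 separates pulmonary from non-pulmonary failure, and the criterion for proceeding is pulmonary. A reader might infer that oxygenation is buried in a multi-organ sum. The text does not support that. It leaves the choice open, and if the respiratory item is used the loss ranges from negligible to moderate, depending on cut-points.

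Second, Aims 1 and 3 frame the lung hypothesis as "Improvement in pulmonary organ function based on requirements for oxygen and advanced respiratory support", and the matching outcomes are listed and not confined to 72 hours. On days 3 and 4 the concordant lower quartile is already 21%, which is room air, so time to stopping oxygen bears directly on the Table 2 signal. It would be wrong to say that the plan has no lung outcome able to show it. These outcomes do, however, give one value per patient, and both Aim 2 and the decision rule speak of a trajectory.

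Third, a reader might infer that a 72-hour end misses the signal. If ICU admission is day 1, then 48 and 72 hours are days 3 and 4, the two strongest days, and only day 5 is lost. If day n means n x 24 hours, days 4 and 5 are lost. The documents do not define it, so the end time is a secondary point.

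Fourth, the protocol disclaims power for patient-centred outcomes, and continuous SpO2/FiO2 would itself often miss the effect. That stands. The case for the change rests on estimation and on a pre-stated score, not on reaching significance.

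Fifth, Table 2 is a retrospective concordance contrast, not titrated dosing against usual care. Table 1 also describes a retrospective ICU cohort, and its SOFA spread already includes the lung. The trial excludes refractory septic shock, which may narrow other-organ variation. The power figures are therefore illustrative.

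**Conclusion.** The point holds as a gap in specification with an inexpensive improvement available. The score behind the pulmonary trajectory is not named, the continuous ratio is not analysed, and scheduled follow-up is shorter than that of CRP.

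The size depends on which score would be used. Moving from the total to continuous SpO2/FiO2 raises single-day power on days 3-4 from about 6-16% to about 37-55%. Moving from the respiratory item, at about 23-54%, gains anywhere from almost nothing to a moderate amount. The figures rest on 22 per arm, two-sided 0.05, the Table 2 quartiles, and assumed cut-points and other-organ spread.

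The stronger conclusion, that the plan could hardly detect its own signal because of the measure chosen, is not supported. It would be true of the total only, and much of the low power comes from enrolling 44. The primary outcome, feasibility, is unaffected.

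**What to change.** - In section IV.B, add SpO2/FiO2 at randomisation and each morning through day 5 as a continuous secondary outcome, and define how study days are counted.
- In section IV.f, compare arms by a repeated-measures linear model adjusted for the randomisation value, and report the estimate with a confidence interval.
- In the decision to proceed, name that estimate as the pulmonary element.
- Report respiratory and non-respiratory SOFA separately, which matches the wording of Aim 2.
- State in advance how values after death or discharge enter the analysis, with a sensitivity analysis. One option is a room-air value after discharge and the worst value after death. That turns the outcome into a composite and should be described as one.

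The cost is wording plus a few charted values per patient beyond those that SOFA already needs, with no new test. The handling of death and discharge is the one real complication.

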This pilot study is being conducted to assess the feasibility of recruiting patients and clinician adherence to steroid protocol, to refine the trial intervention and endpoints, and to calculate target sample sizes in preparation for a larger pragmatic clinical trial comparing the two approaches to corticosteroid administration.

Specific Aim 2: To evaluate the trajectories of C-reactive protein (CRP), pulmonary and non-pulmonary organ failures over time in patients from the two study arms.

In addition to assessing the feasibility of individualized, biomarker guided steroid dosing, this pilot study is necessary to evaluate the usefulness of CRP as a predictive enrichment tool in identifying patients in whom steroid administration will be most beneficial and also as a prognostic enrichment tool (alongside severity of pulmonary and other organ failures) to identify patients at higher risk of poor outcomes. It will inform the target population and will help refine the thresholds for initiation, titration and discontinuation of individualized corticosteroid therapy used to reduce inflammation in patients with pneumonia and acute hypoxic respiratory failure

Specific Aim 3: To evaluate the role of a biomarker-titrated adjuvant corticosteroid administration compared to usual care in patients admitted to hospital with SARS Co-V 2 (COVID-19) infection. We hypothesize that, compared to usual care, individualized biomarker-titrated dosing will be associated with:

- a) Improvement in pulmonary organ function based on requirements for oxygen and advanced respiratory support

- b) Reduced hospital length of stay
- c) Reduced cardiovascular complications including evidence of myocardial injury, need for inotropes and new/worsening arrhythmias

II. Background and Significance

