In response to the emerging COVID-19 (SARS Co-V 2) pandemic, we additionally propose evaluating the role of biomarker-titrated adjuvant corticosteroid dosing in patients with COVID-19. Limited data exists regarding the role of corticosteroids in this setting, and no biomarker-titrated steroid administration has been studied. In a report of 149 patients with COVID-19 in China, 82 had elevated CRP⁽¹⁴⁾. However, just 5 patients received corticosteroids in this cohort. In a larger cohort of 1099 patients with COVID-19 in Wuhan, China, 204 patients received steroids, with a higher percentage among those with severe disease than non-severe disease (44.5% vs. 13.7%)⁽¹⁵⁾. Relative survival of those who received steroids versus those who did not was not reported. In another series of 52 patients with severe COVID-19 infection in China, corticosteroids were administered in 30 patients (58%)⁽¹⁶⁾. Survivors were more likely to receive steroids compared to non-survivors (70% versus 50%).

Furthermore, there is mounting evidence of cardiovascular complications of SARS-CoV-2 infection including acute myocardial injury, shock and arrhythmias associated with worse outcomes⁽¹⁷⁾. Potential mechanisms of these complications in SARS-CoV-2 infection include exaggerated systemic inflammatory responses, cor pulmonale due to respiratory failure and direct myocardial toxicity/myocarditis thus rational therapeutic options should include anti-inflammatory agents like corticosteroids, antiviral agents, and management of respiratory failure.

Given the limited evidence of adjuvant steroid dosing in this setting, and the absence of any proven treatments for COVID-19, there is an urgent need to evaluate any potential therapies.

III. Progress Report and Preliminary Studies

We performed a retrospective review of patients admitted to the intensive care unit (ICU) at Mayo Clinic, Rochester with pneumonia and acute hypoxemic respiratory failure. In this group, we described current corticosteroid prescribing practices, and compared the efficacy and safety of steroid administration that is biomarker concordant (i.e. patients with a markedly elevated

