h. Strengths – This is a well-designed pilot study to examine the feasibility of this approach. Data from this study, including estimated effects of the intervention and sample variation in outcomes, will provide valuable information to plan a well-powered subsequent phase II/III trial.

i. Limitation – Subject enrollment is dependent on availability of research coordinators, therefore we aim to enroll 44 patients within a 2 year period. Randomization by stratification might limit wide generalizability and feasibility if a high proportion of subjects with chronic obstructive lung disease are enrolled. We also acknowledge the fact that the lack of blinding of treating attending physicians and physicians in training is a strong limitation in our study.

V. Human Subjects

Informed consent: All subjects for this study will be provided a consent form describing this study and providing sufficient information for subjects to make an informed decision about their participation in this study. This consent form will be submitted with the protocol for review and approval by the IRB for the study.

The risk profile would justify deferred consent for those who are unable to give consent and have no legally authorized representative available within the short timeframe.

Our inclusion and exclusion criteria have been carefully selected to maximize potential benefit and minimize risk to study subjects.

For suspected/confirmed COVID-19 subjects: Due to the high infectivity of COVID-19, and the strict need to minimize contact between suspected COVID-19 patients and study staff, we propose consent be obtained verbally via telephone or via video.

Patients would still receive a copy of the consent form describing the study. This would be given to the patient by the room nurse to be coordinated with other routine cares.

For all other subjects: The consent form must be signed by the subject or the subject's legally authorized representative, and the individual obtaining the informed consent.

Potential risks: We will include a detailed description of potential risks and benefits of corticosteroid administration while obtaining patient consent.

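### The troponin part of the myocardial injury outcome has no cut-off, scale or entry reference, so injury already present at randomisation is mixed into an outcome meant to show a reduction

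*Combined protocol and SAP*

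**What the plan says.** The outcome is in the secondary outcomes list of the Research Design and Methods section: "Evidence of myocardial injury determined by daily troponin peak and/or new diagnosis of LV dysfunction", with a further alternative of a "new diagnosis of cor pulmonale". The item just above it is "New onset/worsening arrhythmias". Newness is thus required of the left- and right-ventricular components and of arrhythmias (where worsening also counts), but not of troponin.

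The outcome serves Specific Aim 3, hypothesis (c), which concerns COVID-19 patients: "Reduced cardiovascular complications including evidence of myocardial injury, need for inotropes and new/worsening arrhythmias".

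On sampling, the Protocol paragraphs say only "Daily Troponin measurements will be added in both arms". They give no start, no duration and no sample before randomisation. The exclusion criteria do not remove patients with raised troponin or cardiac injury at entry. For Aims 1 and 3 the Data Analysis section says "Continuous outcomes will be compared between treatment arms using linear regression and binary outcomes using chi-square or fishers exact tests", and names no baseline covariate.

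**The concern.** Aim 3(c) is about complications that treatment might prevent. A patient whose highest troponin is the first value, falling thereafter, had the injury before the assigned strategy could act. Nothing in the definition separates that patient from one whose troponin rises on study.

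Injury at entry is plausible from the protocol's own reasoning. Its Background says "Potential mechanisms of these complications in SARS-CoV-2 infection include exaggerated systemic inflammatory responses, cor pulmonale due to respiratory failure", and acute respiratory failure is the entry condition.

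Randomisation balances entry injury between arms on average, so it tends to hide a real effect and add noise. This matters because the Sample Size and Power section intends the pilot data to supply effect sizes for planning the next trial.

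**Working it through.** The plan states no event rate, effect size or power for this outcome, so there is no figure to reproduce. The rates below are assumptions chosen to show direction and scale.

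**Peak scored yes/no.** Let b be the share with troponin above the (unstated) cut-off at entry, and p the rate of new injury among the rest. If entry cases always count and treatment cannot undo them:

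- observed rate = b + (1 - b) × p
- observed risk difference = (1 - b) × true risk difference

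With p = 30% in usual care and 15% in the biomarker arm (difference 15 points, risk ratio 0.50):

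| b | Usual care | Biomarker arm | Difference (points) | Risk ratio |
|---|---|---|---|---|
| 10% | 0.10 + 0.90 × 0.30 = 37% | 0.10 + 0.90 × 0.15 = 23.5% | 13.5 | 0.64 |
| 20% | 0.20 + 0.80 × 0.30 = 44% | 0.20 + 0.80 × 0.15 = 32% | 12 | 0.73 |
| 40% | 0.40 + 0.60 × 0.30 = 58% | 0.40 + 0.60 × 0.15 = 49% | 9 | 0.84 |

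With lower assumed rates, 20% v 10%, the risk ratio of 0.50 becomes 0.68, 0.78 and 0.88.

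**Effect on planning the next trial.** Assumptions: two-sided 5% test of two proportions, 80% power, 1:1 allocation. The right-hand columns count only new injury among patients free of it at entry. The number needed with no entry injury (121 per arm for 30% v 15%, 199 for 20% v 10%) is divided by (1 - b) to give patients enrolled.

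| b | 30% v 15%: as written | 30% v 15%: new only | 20% v 10%: as written | 20% v 10%: new only |
|---|---|---|---|---|
| 10% | 181 | 135 | 348 | 222 |
| 20% | 256 | 152 | 533 | 249 |
| 40% | 481 | 202 | 1089 | 332 |

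All figures are per arm.

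**Peak analysed as a value.** The table of rates does not apply. If the correlation between entry troponin and later peak is r, adjusting for the entry value in the linear regression leaves a fraction 1 - r² of the variance. For an assumed r of 0.5 this is 1 - 0.25 = 0.75, and for 0.7 it is 1 - 0.49 = 0.51. Leaving the entry value out therefore forgoes a variance reduction of 25% to 49%. A peak that occurs at entry also cannot respond to treatment.

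**The case against.** The strongest reply is that the plan contains no scoring rule. A peak is naturally a number, and linear regression is planned for continuous outcomes. A reader might infer that every raised troponin is counted as an event; the documents do not say so, and the risk ratios above hold only under yes/no scoring. That limits the arithmetic but does not remove the gap: cut-off, scale and entry reference are all missing, and each reading has a cost.

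Entry injury is also not documented. The Background speaks only of potential mechanisms, and no prevalence is given. The formula further treats a patient already raised at entry as unable to respond, although such a patient could rise further. So the direction follows from the definition, but the size is unknown.

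The daily series would show whether the first value was the highest, so the problem is partly recoverable if a rise rule is fixed before analysis. A first on-study value is still not an entry value.

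Finally, the stakes are modest. The protocol disclaims power for efficacy, intends the pilot partly to refine its endpoints, and does not list this outcome among the criteria for proceeding to a larger study. Even if all 44 patients were split equally, power for 30% v 15% would be about 22% with no entry injury at all. This limits the consequence but does not excuse passing a diluted effect size forward.

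**Conclusion.** The concern holds as a gap in the outcome definition. The troponin component lacks a cut-off, a scale and an entry reference, and no other section supplies them. Under yes/no scoring the risk difference is multiplied by (1 - b); for 30% v 15% the risk ratio moves from 0.50 to between 0.64 and 0.84 for b from 10% to 40%. Under continuous analysis the cost is lost precision. The rates, prevalences and correlations are all assumed.

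The documents do not support three stronger inferences that a reader might draw:

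- **Bias towards one arm.** Entry injury is balanced on average, so the effect is attenuation and noise.
- **An event rate that is mostly baseline prevalence.** At b = 10%, entry cases are 10/37 = 27% of usual-care events and 10/23.5 = 43% of biomarker-arm events. At 20% they are 20/44 = 45% and 20/32 = 62.5%. They are the majority in both arms only in the 40% scenario (40/58 = 69% and 40/49 = 82%).
- **A comparison of 22 v 22 for Aim 3(c).** The protocol says "we aim to enroll 44 patients within a 2 year period" for the whole trial and gives neither an allocation ratio nor a size for the COVID-19 stratum.

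The consequence is limited to Aim 3(c) and to the effect size carried into the next trial.

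**What to change.** - Take a troponin at or before randomisation in both arms, as an add-on to the admission or consent-day sample.
- State the cut-off, and whether the component is scored yes/no or analysed as a value.
- If yes/no, count only events after randomisation: a value above the cut-off where the entry value was below it, or a prespecified further rise where it was already above.
- If continuous, use the post-randomisation peak and add the entry value as a covariate in the linear regression already planned.
- Report entry injury by arm as a baseline characteristic.

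The cost is one troponin and a few lines of definition. Troponin is already to be drawn daily, and the Human Subjects section already allows for a possible extra blood draw on the day of consent. The downside is fewer counted events. If the entry sample can no longer be added, a rise rule based on the first daily value, fixed before analysis, is a weaker substitute.
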